6.1.4. Part A (Phase 1; dose escalation): Extended Treatment Phase

Time-point: From Cycle 3 onwards (every 14 days \pm 2 days)

Note: On the day of dosing, all procedures to be performed pre-dose.

- Vital signs
- AEs
- Concomitant medications
- Mandatory biopsy (end of Cycle 2/beginning of Cycle 3 if treatment is extended)
- Physical examination
- ECOG
- Weight assessment (every 2 weeks)
- ECG (only every 4 weeks)
- Safety laboratory testing (hematology, clinical chemistry, coagulation) (within 24 hours prior to dosing)
- Safety urine analysis
- Urine pregnancy test (if positive, to be confirmed with serum test), (prior to any treatment with CTL-002)

- Immune monitoring (cytokines/chemokines) (only in Cycle 3)
- PK: Sample taken within 30 minutes prior infusion and immediately before end of infusion (1 hour)
- Serum analysis of GDF-15: Sample taken within 30 minutes prior to infusion and immediately before end of infusion (1 hour)
- Immunogenicity/ADA testing (only Cycle 3-5)
- Blood molecular/transcriptional profiling: Sample taken within 30 min prior to CTL-002 infusion (only Cycle 3-4)
- Assessment of thyroid hormones, HbA1c and NT-proBNP (every 2 weeks for 3 months, thereafter monthly)
- Tumor assessment/Imaging: CT/MRI/PET-Scan to document tumor burden according to RECIST/iRECIST (Refer to [Appendix 2](#)): after 8 weeks and every 8 weeks thereafter; End of Treatment Visit only if last scan is more than 4 weeks old
- L3SMI (every 8 weeks)
- MCASCO (every 4 weeks)
- Cutaneous tumor lesion assessment/photography (every 4 weeks)
- CTL-002 infusion over approximately 60 minutes (\pm 10 min) - prior to any nivolumab infusion
- Nivolumab infusion over approximately 30 minutes (\pm 5 min)

6.1.5. Part B (Phase 2a; expansion), All Cohorts Except Cutaneous Squamous-Cell Carcinoma: Core Treatment Period – Nivolumab Combination (Cycles 1-4)

Time-point: After confirmation of all study eligibility criteria – Cycles 1 to 4

Note: On the day of study drug dosing, all procedures are to be performed pre-dose. Before start of first CTL-002 infusion, safety laboratory parameters will be assessed to reconfirm eligibility and ability to receive study treatment.

Cycle 1

Week 1: Day 1

- Medical history/current medical conditions, prior cancer therapies including radiation and surgery
- AEs
- Concomitant medications
- Physical examination
- ECOG Performance Status
- ECG, (in extended treatment only every 4 weeks)
- Safety laboratory testing (hematology, clinical chemistry, coagulation): Pre-CTL-002 infusion (within 24 hours prior to dosing to reconfirm eligibility criteria) and 6 hours after the start of CTL-002 infusion.
- Safety urinalysis
- Urine pregnancy test (mandatory for women of childbearing potential). If positive, confirm with serum test (prior to any treatment with study drug)

- Immune monitoring (cytokines/chemokines): Sample taken within 30 minutes prior to CTL-002 infusion
- PK: Sample taken within 30 minutes prior to CTL-002 infusion, and immediately before the end of CTL-002 infusion (1 hour).
- Serum analysis of GDF-15: Sample taken within 30 minutes prior to CTL-002 infusion.
- Immunogenicity/ADA: Sample taken within 30 minutes prior to CTL-002 infusion
- Blood molecular/transcriptional profiling: Sample taken within 30 min prior to CTL-002 infusion
- Vital Signs including systolic and diastolic blood pressure (sitting), pulse rate, temperature, respiratory rate, and oxygen saturation immediately before CTL-002 infusion and then 15 min (\pm 5 min), 30 min (\pm 5 min), 60 min (\pm 15 min), 90 min (\pm 15 min), 2 hrs (\pm 15 min), and 4 hrs (\pm 15 min) after the start of CTL-002 infusion
- Immediate combination treatment (no prior monotherapy cycle):
 - CTL-002 infusion over approximately 60 minutes (\pm 10 min) - 30 minutes before nivolumab infusion
 - Nivolumab infusion over approximately 30 minutes (\pm 5 min)
- Overnight hospitalization/observation

Week 1: Day 2

- Vital signs including systolic and diastolic blood pressure (sitting), pulse rate, temperature, respiratory rate, and oxygen saturation
- AEs
- Concomitant medications
- Safety laboratory testing (hematology, clinical chemistry, coagulation)
- Immune monitoring (cytokines/chemokines): Sample taken 24 hours (\pm 2 hours) post-CTL-002 infusion
- PK: Sample taken at 24-hour (\pm 2 hours) after start of CTL-002 infusion
- Serum analysis of GDF-15: Sample taken 24 hours (\pm 2 hours) after start of CTL-002 infusion

Week 2: Day 8 (\pm 24 hours)

- Vital signs including systolic and diastolic blood pressure (sitting), pulse rate, temperature, respiratory rate, and oxygen saturation
- AEs
- Concomitant medications
- Physical examination
- ECOG Performance Status
- Safety laboratory testing (hematology, clinical chemistry, coagulation)
- PK: Sample taken at Day 8 (\pm 24 hours)
- Serum analysis of GDF-15: Sample taken at Day 8 (\pm 24 hours)

Cycle 2

Week 3: Day 1 (\pm 2 days)

Note: On the day of dosing, all procedures to be performed pre-dose.

- AEs
- Concomitant medications
- Physical examination
- ECOG Performance Status
- Weight assessment
- Safety laboratory testing (hematology, clinical chemistry, coagulation) (within 24 hours prior to dosing)
- Assessment of thyroid hormones, HbA1c, and NT-proBNP
- Urine pregnancy test (mandatory for women of childbearing potential). If positive, confirm with serum test (prior to any treatment with study drug)
- Immune monitoring (cytokines/chemokines): Sample taken within 30 minutes prior to CTL-002 infusion
- PK: Sample taken within 30 minutes prior to CTL-002 infusion and immediately before end of CTL-002 infusion (1 hour)
- Serum analysis of GDF-15: Sample taken within 30 minutes prior to CTL-002 infusion
- Immunogenicity/ADA: Sample taken within 30 minutes prior to CTL-002 infusion
- Vital signs including systolic and diastolic blood pressure (sitting), pulse rate, temperature, respiratory rate, and oxygen saturation (immediately before CTL-002 infusion)
- Combination treatment:
 - CTL-002 infusion over approximately 60 minutes (\pm 10 min) - prior to any nivolumab infusion
 - Nivolumab infusion over approximately 30 minutes (\pm 5 min)

Cycle 3-4: Day 1 (\pm 2 days)

Time-point: From Cycle 3-4 (every 14 days \pm 2 days)

Note: On the day of dosing, all procedures to be performed pre-dose.

- Vital signs including systolic and diastolic blood pressure (sitting), pulse rate, temperature, respiratory rate, and oxygen saturation (immediately before CTL-002 infusion)
- AEs
- Concomitant medications
- Mandatory biopsy (only for melanoma; end of Cycle 4/beginning of Cycle 5)
- Physical examination
- ECOG Performance Status
- Weight assessment (every 2weeks)
- ECG (only every 4 weeks)
- Safety laboratory testing (hematology, clinical chemistry, coagulation) (within 24 hours prior to dosing)
- Assessment of thyroid hormones, HbA1c, and NT-proBNP (every 2 weeks for 3 months, thereafter monthly)

- Urine pregnancy test (mandatory for women of childbearing potential). If positive, confirm with serum test) (prior to any treatment with study drug)
- Immune monitoring (cytokines/chemokines) (only in Cycle 3)
- PK: Sample taken within 30 minutes prior infusion and immediately before end of infusion (1 hour)
- Serum analysis of GDF-15: Sample taken within 30 minutes prior to infusion
- Immunogenicity/ADA testing
- Tumor assessment/Imaging: CT/MRI/PET-Scan to document tumor burden according to RECIST/iRECIST (refer to [Appendix 2](#)): after 8 weeks and every 8 weeks thereafter
- Cutaneous tumor lesion assessment/photography (every 4 weeks)
- Combination treatment:
 - CTL-002 infusion over approximately 60 minutes (\pm 10 min) - prior to any nivolumab infusion
 - Nivolumab infusion over approximately 30 minutes (\pm 5 min)

6.1.6. Part B (Phase 2a; expansion), All Cohorts Except Cutaneous Squamous-Cell Carcinoma: Extended Treatment Phase - Nivolumab Combination

Time-point: From Cycle 5 onwards (every 14 days \pm 2 days)

Note: On the day of dosing, all procedures to be performed pre-dose.

- Vital signs including systolic and diastolic blood pressure (sitting), pulse rate, temperature, respiratory rate, and oxygen saturation
- AEs
- Concomitant medications
- Physical examination
- ECOG Performance Status
- Weight assessment (every 2 weeks)
- ECG (only every 4 weeks)
- Safety laboratory testing (hematology, clinical chemistry, coagulation) (within 24 hours prior to dosing)
- Assessment of thyroid hormones, HbA1c, and NT-proBNP (every 2 weeks for 3 months, thereafter monthly)
- Safety urine analysis (only every 8 weeks)
- Urine pregnancy test (mandatory for women of childbearing potential). If positive, confirm with serum test (prior to any treatment with study drug)
- PK: Sample taken within 30 minutes prior infusion and immediately before end of infusion (1 hour)
- Serum analysis of GDF-15: Sample taken within 30 minutes prior to infusion
- Immunogenicity/ADA testing (Cycle 5 only)
- Blood molecular/transcriptional profiling: Sample taken within 30 min prior to CTL-002 infusion (only Cycle 5 [after 8 weeks] and Cycle 9 [after 16 weeks])

- Tumor assessment/Imaging: CT/MRI/PET-Scan to document tumor burden according to RECIST/iRECIST (Refer to [Appendix 2](#)): after 8 weeks and every 8 weeks thereafter; End of Treatment Visit only if last scan is more than 4 weeks old
- Cutaneous tumor lesion assessment/photography (every 4 weeks)
- Mandatory biopsy (for melanoma and the biomarker cohort with mixed solid tumors; end of Cycle 4/beginning of Cycle 5)
- Combination treatment:
 - CTL-002 infusion over approximately 60 minutes (\pm 10 min) prior to any nivolumab infusion
 - Nivolumab infusion over approximately 30 minutes (\pm 5 min)

6.1.7. Part B (Phase 2a; Expansion), Cutaneous Squamous-Cell Carcinoma Cohort: Core Treatment Period – Cemiplimab Combination (Cycles 1-3)

Time-point: After confirmation of all study eligibility criteria – Cycles 1 to 3

Note: On the day of study drug dosing, all procedures are to be performed pre-dose. Before start of first CTL-002 infusion, safety laboratory parameters will be assessed to reconfirm eligibility and ability to receive study treatment.

Cycle 1

Week 1: Day 1

- Medical history/current medical conditions
- AEs
- Concomitant medications
- Physical examination
- ECOG Performance Status
- ECG
- Safety laboratory testing (hematology, clinical chemistry, coagulation): Pre-CTL-002 infusion (within 24 hours prior to dosing to reconfirm eligibility criteria) and 6 hours after the start of CTL-002 infusion.
- Safety urinalysis
- Urine pregnancy test (mandatory for women of childbearing potential). If positive, confirm with serum test (prior to any treatment with study drug)
- Immune monitoring (cytokines/chemokines): Sample taken within 30 minutes prior to CTL-002 infusion
- PK: Sample taken within 30 minutes prior to CTL-002 infusion, and immediately before the end of CTL-002 infusion (1 hour).
- Serum analysis of GDF-15: Sample taken within 30 minutes prior to CTL-002 infusion.
- Immunogenicity/ADA: Sample taken within 30 minutes prior to CTL-002 infusion
- Blood molecular/transcriptional profiling: Sample taken within 30 min prior to CTL-002 infusion
- Vital Signs including systolic and diastolic blood pressure (sitting), pulse rate, temperature, respiratory rate, and oxygen saturation immediately before CTL002 infusion and then

15 min (\pm 5 min), 30 min (\pm 5 min), 60 min (\pm 15 min), 90 min (\pm 15 min), 2 hrs (\pm 15 min), and 4 hrs (\pm 15 min) after the start of CTL-002 infusion

- Immediate combination treatment (no prior monotherapy cycle):
 - CTL-002 infusion over approximately 60 minutes (\pm 10 min); 30 minutes before cemiplimab infusion
 - Cemiplimab infusion over approximately 30 minutes (\pm 5 min)
- Overnight hospitalization/observation

Week 1: Day 2

- Vital signs including systolic and diastolic blood pressure (sitting), pulse rate, temperature, respiratory rate, and oxygen saturation
- AEs
- Concomitant medications
- Safety laboratory testing (hematology, clinical chemistry, coagulation)
- Immune monitoring (cytokines/chemokines): Sample taken 24 hours (\pm 2 hours) post-CTL-002 infusion
- PK: Sample taken at 24-hour (\pm 2 hours) after start of CTL-002 infusion
- Serum analysis of GDF-15: Sample taken 24 hours (\pm 2 hours) after start of CTL-002 infusion

Week 2: Day 8 (\pm 24 hours)

- Vital signs including systolic and diastolic blood pressure (sitting), pulse rate, temperature, respiratory rate, and oxygen saturation
- AEs
- Concomitant medications
- Physical examination
- ECOG Performance Status
- Safety laboratory testing (hematology, clinical chemistry, coagulation)
- PK: Sample taken at Day 8 (\pm 24 hours)
- Serum analysis of GDF-15: Sample taken at Day 8 (\pm 24 hours)

Cycle 2

Week 4: Day 1 (\pm 2 days)

Note: On the day of dosing, all procedures to be performed pre-dose.

- AEs
- Concomitant medications
- Physical examination
- ECOG Performance Status
- Weight assessment
- Safety laboratory testing (hematology, clinical chemistry, coagulation)
- Assessment of thyroid hormones, HbA1c, and NT-proBNP

- Urine pregnancy test (mandatory for women of childbearing potential). If positive, confirm with serum test (prior to any treatment with study drug)
- Immune monitoring (cytokines/chemokines): Sample taken within 30 minutes prior to CTL-002 infusion
- PK: Sample taken within 30 minutes prior to CTL002 infusion and immediately before end of CTL-002 infusion (1 hour)
- Serum analysis of GDF-15: Sample taken within 30 minutes prior to CTL-002 infusion
- Immunogenicity/ADA: Sample taken within 30 minutes prior to CTL-002 infusion
- Vital signs including systolic and diastolic blood pressure (sitting), pulse rate, temperature, respiratory rate, and oxygen saturation (immediately before CTL-002 infusion)
- Combination treatment:
 - CTL-002 infusion over approximately 60 minutes (\pm 10 min) - prior to any cemiplimab infusion
 - Cemiplimab infusion over approximately 30 minutes (\pm 5 min)

Cycle 3: Day 1 (\pm 2 days)

Week 7: Day 1 (\pm 2 days)

Note: On the day of dosing, all procedures to be performed pre-dose.

- Vital signs including systolic and diastolic blood pressure (sitting), pulse rate, temperature, respiratory rate, and oxygen saturation (immediately before CTL-002 infusion)
- AEs
- Concomitant medications
- Mandatory biopsy (end of Cycle 3/beginning of Cycle 4)
- Physical examination
- ECOG Performance Status
- Weight assessment
- ECG
- Safety laboratory testing (hematology, clinical chemistry, coagulation)
- Assessment of thyroid hormones, HbA1c, and NT-proBNP
- Urine pregnancy test (mandatory for women of childbearing potential). If positive, confirm with serum test (prior to any treatment with study drug)
- PK: Sample taken within 30 minutes prior infusion and immediately before end of infusion (1 hour)
- Serum analysis of GDF-15: Sample taken within 30 minutes prior to infusion
- Immunogenicity/ADA testing
- Tumor assessment/Imaging: CT/MRI/PET-Scan to document tumor burden according to RECIST/iRECIST (refer to [Appendix 2](#)): after 6-9 weeks and every 6-9 weeks thereafter
- Cutaneous tumor lesion assessment/photography (every 6-9 weeks)
- Combination treatment:
 - CTL-002 infusion over approximately 60 minutes (\pm 10 min) - prior to any cemiplimab infusion
 - Cemiplimab infusion over approximately 30 minutes (\pm 5 min)

6.1.8. Part B (Phase 2a; Expansion), Cutaneous Squamous-Cell Carcinoma Cohort: Extended Treatment Phase – Cemiplimab Combination

Time-point: From Cycle 4 onwards (every 21 days \pm 2 days)

Note: On the day of dosing, all procedures to be performed pre-dose.

- Vital signs including systolic and diastolic blood pressure (sitting), pulse rate, temperature, respiratory rate, and oxygen saturation
- AEs
- Concomitant medications
- Physical examination
- ECOG Performance Status
- Weight assessment (every 3 weeks)
- ECG (only every 6 weeks)
- Safety laboratory testing (hematology, clinical chemistry, coagulation)
- Assessment of thyroid hormones, HbA1c, and NT-proBNP (every 3 weeks for 3 months, thereafter every second cycle)
- Safety urine analysis (only every 9 weeks)
- Urine pregnancy test (mandatory for women of childbearing potential). If positive, confirm with serum test (prior to any treatment with study drug)
- PK: Sample taken within 30 minutes prior infusion and immediately before end of infusion (1 hour)
- Serum analysis of GDF-15: Sample taken within 30 minutes prior to infusion
- Immunogenicity/ADA testing (Cycle 4 and 5 only)
- Blood molecular/transcriptional profiling: Sample taken within 30 min prior to CTL-002 infusion (only Cycle 4 [after 9 weeks] and Cycle 7 [after 18 weeks])
- Tumor assessment/Imaging: CT/MRI/PET-Scan to document tumor burden according to RECIST/iRECIST (Refer to [Appendix 2](#)): after 6-9 weeks and every 8-9 weeks thereafter; End of Treatment Visit only if last scan is more than 4 weeks old
- Cutaneous tumor lesion assessment/photography (every 6-9 weeks, according to local practice)
- Mandatory biopsy (end of Cycle 3/beginning of Cycle 4): for cutaneous squamous-cell carcinoma, multiple punch biopsies to be taken (as per clinical possibility, ideally 3-5)
- Combination treatment:
 - CTL-002 infusion over approximately 60 minutes (\pm 10 min) - prior to any cemiplimab infusion
 - Cemiplimab infusion over approximately 30 minutes (\pm 5 min)

6.1.9. End of Treatment Visit

Time-point: 2 weeks after the last CTL-002 infusion (\pm 2 days)

- Vital signs
- AEs
- Concomitant medications
- Physical examination (including neurological examination [check for motor neuropathy])

- ECOG Performance Status
- Weight assessment
- SARS-CoV-2 (COVID-19) testing (RNA and antibody testing)
- Safety laboratory testing (hematology, clinical chemistry, coagulation)
- Assessment of thyroid hormones, HbA1c, and NT-proBNP
- Safety urine analysis
- Urine analysis of GDF-15 (Part A only)
- Urine pregnancy test (if positive, confirm with serum test)
- Immune monitoring (cytokines/chemokines)
- PK
- Serum analysis of GDF-15
- Immunogenicity/ADA testing
- Blood molecular/transcriptional profiling (Part A only)
- Infectious diseases/serology
- Immunoglobulins
- Tumor assessment/Imaging: CT/MRI/PET-Scan to document tumor burden according to RECIST/iRECIST (Refer to [Appendix 2](#)): End of Treatment Visit only if last scan is more than 4 weeks old
- L3SMI (only if last scan is more than 4 weeks old) (Part A only)
- MCASCO (Part A only)
- Cutaneous tumor lesion assessment/photography
- ECG
- Echocardiography or MUGA if ECHO cannot be performed

6.1.10. Safety Follow-up Visit

Time-point: 30 days post last infusion (± 2 days)

- Vital signs
- AEs
- Concomitant medications
- Safety laboratory testing (hematology, clinical chemistry, coagulation)
- Urine pregnancy test (if positive, to be confirmed with serum test)
- Physical examination (including neurological examination [check for motor neuropathy])
- ECOG Performance Status

6.1.11. Follow-up

Time-point: Every 3 months (± 2 weeks) e.g., by phone/email for a total of 12 months in Part A (Phase 1; dose escalation) and a total of 24 months in Part B (Phase 2a; expansion).

- AEs (related to CTL-002 or study procedures)
- Concomitant medications (anti-cancer medication or due to related AEs)
- Cutaneous tumor lesion assessment/photography according to site practices
- Tumor assessment/Imaging: CT/MRI/PET-Scan according to local practice

- Survival

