5.4.2. Recording of Concomitant Medication

Any concomitant treatment and medication information will be collected from the time that subjects sign the ICF until:

- 30 days following the last CTL-002/anti-PD-1 checkpoint inhibitor infusion
- Concomitant medications given to treat AEs deemed related to CTL-002/defined anti-PD-1 checkpoint inhibitor will be recorded up to 12 months (Part A) or 24 months (Part B) following the last CTL-002/ defined anti-PD-1 checkpoint inhibitor infusion or longer in case the AE has not resolved
- Concomitant therapies given to manage a subject's underlying disease will be recorded through the end of the study

Any medication a subject receives at the time of signing the ICF or during the study as well as any changes thereof must be recorded in the eCRF along with:

- Generic name of the drug (or trade name for combination drugs)
- Reason for use
- Dates of administration including start and end dates
- Dosage information including dose and frequency

The Medical Monitor should be contacted if there are any questions regarding concomitant medication or prior therapy.

In addition, any prior or concomitant diseases and signs and symptoms (a condition that is either active at enrolment or adversely impacts the subject's condition at enrolment), if applicable at baseline will be recorded. The Sponsor will code according to the standard dictionaries (e.g., WHO Drug and Medical Dictionary for Regulatory Activities [MedDRA]); for details refer to the Safety Management Plan.

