- (29) Tumor biopsy: baseline biopsy in all subjects (new or archived if obtained within 120 days prior to treatment start); a sequential follow-up biopsy only for melanoma, and the biomarker cohort with mixed solid tumors: baseline biopsy ideally within -7 days before infusion of CTL-002 and second biopsy after 8 weeks of treatment (end of Cycle 4/beginning of Cycle 5). In case the second biopsy is non-evaluable, an optional third biopsy can be collected at the next medically feasible timepoint during ongoing treatment and as per treating physician's decision. If stereotactic radiotherapy is initiated, another follow-up biopsy after 4 wks of the initiation of radiotherapy should be performed. **Note:** All biopsies are to be performed only if seen as safe and feasible from treating physician's discretion.
- (30) Tumor mutational status: Collection of historical data e.g., but not limited to BRAF, CEA, PSA, CA19-9, CA-125, MSI, PD-L1, EGFR, Alk, HER2 and other molecular hallmark changes depending upon subject primary cancer.
- (31) For subjects enrolled under this version of the protocol and under previous protocols v4.0 and 5.0, an optional retrospective analysis of PD-L1 and other relevant biomarkers might be conducted on archival tumor tissue any time after Screening provided and that the subject agrees in writing to this testing.
- (32) After 6 months, only new possibly related AEs will be captured (in addition, SAEs may be reported at any time during the study regardless of relationship).
- (33) Related to CTL-002/defined checkpoint inhibitor or study procedures (in addition, SAEs may be reported at any time during the study regardless of relationship).
- (34) After 6 months, only further anti-cancer-related medication will be captured.
- (35) Anti-cancer medication or medication due to related AEs.
- (36) Every 3 months for 2 years.
- (37) Baseline safety laboratory testing prior to CTL-002 infusion to re-confirm eligibility

Table 7 Schedule of Assessments – Part B (Phase 2a; expansion, combination therapy with cemiplimab (CSCC only))

Examination	Core study								Follow-up	
	Screening	Core Treatment Period					Extended Treatment Period (optional) ⁽¹⁾	End of Treatment Visit	Safety FU/End of Core study	Efficacy and Survival FU
Cycle		Cycle 1			Cycle 2	Cycle 3	Cycle 4-x			
Weeks		Wk 1	Wk 2	Wk 4	Wk 7	3 wk cycle	2 wks post-last CTL-002 infusion	30 d post-last CTL-002 infusion	Every 3 mos for 2 years by phone/(e)mail	

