7. SAFETY REPORTING AND MEDICAL MANAGEMENT

Adverse Events and SAEs, regardless of suspected relationship to study treatment, are recorded from the time the subject consents to the study, to 30 days after last dose.

As part of the safety oversight for this study, in addition to the staggering of subject dosing with CTL-002 in Part A (Phase 1; dose escalation), subjects will only be enrolled and treated with CTL-002 at carefully selected investigational sites who have experience in FIH studies and immunotherapy, handling of related AEs, access to intensive care units (ICU) and immediate and appropriate resuscitation measures at all times during hospitalization.

Medical measures have been implemented which ensures a quick diagnosis of events and the implementation of quick actions (e.g., central venous access, hospitalization, close subject monitoring for vital signs, cardiac monitoring).

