7.2.1. Recording of AEs/SAEs

The Investigator is responsible for ensuring that all AEs that are observed by trial site personnel or reported by a subject, are recorded on the eCRF during the study and/or as described below. All SAEs must be reported using the SAE reporting form.

These AEs will include the following:

- All SAEs (as defined in [Section 7.2.3.1](#)) that occur after the subject has signed the first ICF up to 30 days after last dose of CTL-002/nivolumab/cemiplimab (i.e., the Safety Follow-up/End of Core Study Visit).

Exceptions/additions:

- Serious AEs and non-serious AEs related to study participation/procedures or leading to withdrawal from study that occur after the subject has signed the ICF must be reported until end of study (as defined in [Section 9.5](#)).
- Serious AEs deemed by the Investigator to be at least possibly related to CTL-002/nivolumab that occur from first day of administration (Day 1) until the end of the study (as defined in [Section 9.5](#)).
- DLTs (as defined in [Section 2.2.1.3](#))
- All non-serious AEs (i.e., any AEs that do not meet a serious criteria) that occur from Screening up to 30 days after the last dose of CTL-002/nivolumab/cemiplimab (i.e., the Safety Follow-up Visit).

The AE term should be reported in standard medical terminology when possible: diagnosis or syndrome(s) if known, signs or symptoms can be accepted if underlying cause is not known. For each AE, the Investigator will evaluate and report the onset (date and time), resolution (date and time), intensity, causality, action taken, severity and serious outcome (if applicable), and whether or not it caused the subject to discontinue the study.

The Investigator may be asked to provide follow-up information, discharge summaries, and extracts from medical records or eCRFs.

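### Adverse events starting more than 30 days after the last dose fall under conflicting collection rules, so late non-serious checkpoint-inhibitor-related events are recorded or lost depending on the section a site follows

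*Protocol*

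**What the plan says.** Five places in the Protocol govern events that start after day 30.

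- **Section 6.1.11 (Follow-up).** Contacts run every 3 months "for a total of 12 months in Part A (Phase 1; dose escalation) and a total of 24 months in Part B". The events to be collected are "AEs (related to CTL-002 or study procedures"). The checkpoint inhibitor is not named.
- **Section 6.1.12, Tables 5 to 7.** The footnotes to the follow-up column (Table 5 footnote 39, Table 6 footnote 33, Table 7 footnote 31) read "Related to CTL-002/defined checkpoint inhibitor or study procedures". They add, in permissive wording, that serious events may be reported whatever their relationship.
- **Section 7, lead-in.** Adverse events and serious adverse events "are recorded from the time the subject consents to the study, to 30 days after last dose". No extension is mentioned there.
- **Section 7.2.1.** Non-serious events are those "that occur from Screening up to 30 days after the last dose of CTL-002/nivolumab/cemiplimab". Events related to study participation or procedures, or leading to withdrawal, continue to the end of study. A further bullet extends "Serious AEs deemed by the Investigator to be at least possibly related to CTL-002/nivolumab that occur from first day of administration" to the end of study. Cemiplimab is absent from that bullet, although other bullets in the section name all three drugs.
- **Section 7.2.4.** Any serious event, whatever its relationship and whenever it is discovered, is reported within 24 hours.

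Section 5.4.2 bears on the same events from the medication side: "Concomitant medications given to treat AEs deemed related to CTL-002/defined anti-PD-1 checkpoint inhibitor will be recorded up to 12 months" in Part A, and up to 24 months in Part B.

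**The concern.** The number of subjects with adverse events is a primary endpoint in both parts (Section 1.10.1). Section 8.3.2 summarises every event that starts after exposure and states no upper time limit, so what sites collect largely decides what the tables show. Section 5.2.7.1 warns that immune-related events can appear after checkpoint blockade has stopped, and Section 1.8.1 names potentiation of anti-PD-1 toxicity as a risk to watch. The events on which the rules disagree are therefore of the kind that the safety objective is about.

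An analysis plan can limit the reporting window. It cannot restore events that a site was told not to record. If sites follow different sections, late-event frequencies in different cohorts will rest on different ascertainment, and the database will not show which.

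**Working it through.** This is a comparison of texts. The protocol gives no figure to reproduce. The table takes an event that starts after day 30 and asks whether each place collects it. **Alone** means attributed to that drug and not to CTL-002.

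| Late event | 6.1.11 | Tables 5–7 footnotes | Section 7 lead-in | 7.2.1 | 7.2.4 |
|---|---|---|---|---|---|
| Non-serious, nivolumab or cemiplimab alone | not listed | yes | no | no* | not applicable |
| Non-serious, CTL-002 | yes | yes | no | no* | not applicable |
| Serious, nivolumab alone | not listed | yes | no | yes | yes |
| Serious, cemiplimab alone | not listed | yes | no | not in the related-event bullet* | yes |
| Serious, CTL-002 | yes | yes | no | yes | yes |

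*Unless related to study participation or procedures, or leading to withdrawal.

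Reading the rows:

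1. A non-serious event attributed to the checkpoint inhibitor alone is collected only under the schedule footnotes. Sections 6.1.11 and 7.2.1 both leave it out, and 7.2.4 does not apply.
2. A non-serious event attributed to CTL-002 is collected under 6.1.11 and the footnotes, but not under 7.2.1.
3. Serious events are better protected. Nivolumab-related ones are covered to the end of study by 7.2.1, and all of them by 7.2.4. The defects are the missing cemiplimab and a lead-in that contradicts both.
4. Under Section 5.4.2 a site would record a drug given for a late checkpoint-inhibitor-related event to month 24 in Part B. Under 6.1.11 or 7.2.1 it would not record the non-serious event being treated.
5. Section 7.2.2 asks for relationship to the study treatment and not to each component, so the CTL-002-only filter in 6.1.11 is hard to apply.

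Scale in the cemiplimab cohort, from the sizes in Section 8.1 (12 at the first stage, 12 + 24 = 36 after expansion): one subject moved into or out of a category changes its incidence by 1/12 = 8.3 percentage points, or 1/36 = 2.8 percentage points.

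**The case against.** The best defence is that the intended rule can be found. Section 6.1 makes adherence to the schedules of assessments essential, Tables 5 to 7 agree with one another and with Section 5.4.2, and Section 6.2.4 says that study-related safety is captured through follow-up. A site working from the schedules would collect these events. This shows what was probably meant. It does not remove the narrower instructions in 6.1.11 and in 7.2.1, the section that defines the investigator's recording duty, and no order of precedence is given.

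It can also be said that the participation exception in 7.2.1 might include study treatment. That is possible, but the separate bullet on drug-related serious events would then add little, so the reading is uncertain.

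Third, because CTL-002 and the checkpoint inhibitor are given together and potentiation is suspected, few late events may be attributed to the partner drug alone. This reduces the gap under 6.1.11. It does not help under 7.2.1, where non-serious CTL-002-related events also stop at day 30.

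Two stronger readings are tempting and are not supported. A reader might infer that late cemiplimab-related serious events have no collection rule in Section 7. Section 7.2.4 covers them. A reader might also multiply an assumed late-event rate by the Part B maximum of 249 to estimate the subjects lost. The documents give no such rate, 249 requires every expansion to occur, and the product would count as lost the serious and CTL-002-related events that other sections do collect.

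**Conclusion.** The contradiction stands. After day 30, non-serious events attributed to nivolumab or cemiplimab, and under 7.2.1 those attributed to CTL-002, are recorded or not according to the section followed. Late cemiplimab-related serious events are reportable under 7.2.4 but missing from the 7.2.1 bullet meant for related serious events.

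The consequence is moderate. Subjects with any event before day 31 are already in the any-event count, so that primary count should move little if, as is likely, many subjects have one. The effect falls on frequencies by term, grade and relationship and on late immune-related events. There a single subject is 8.3 points of 12 or 2.8 points of 36 in the cemiplimab cohort. How many subjects are affected cannot be stated from the protocol. The conclusion assumes only that some late treatment-related events occur, which Section 5.2.7.1 anticipates.

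**What to change.** Reconcile Section 6.1.11, the follow-up footnotes of Tables 5 to 7, the Section 7 lead-in, Section 7.2.1 and Section 7.2.4 to one data-collection rule that matches the schedules and Section 5.4.2:

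- From day 31 after the last dose to the end of follow-up, record serious and non-serious events at least possibly related to CTL-002, to the defined checkpoint inhibitor (nivolumab or cemiplimab) or to study procedures.
- Add cemiplimab to the related-serious-event bullet of Section 7.2.1.
- State the end of collection for serious events regardless of relationship, consistently with Section 7.2.4, and replace the permissive footnote wording accordingly.

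The cost is wording in an amendment and a note to sites. The 3-monthly contacts already exist and the schedules already ask for the related events, so no visit is added and no treatment rule changes.
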